Appendix 2: Informed Consent Form

Please see informed consent form.

PAGE LEFT BLANK INTENTIONALLY

Appendix 3: Adverse Event Definitions and Safety Reporting for Investigators (as per requirements for marketed products)

a. Definitions

An Adverse Event/Experience [AE] is any untoward medical occurrence in a subject or clinical study subject administered a medicinal product which does not necessarily have a causal relationship with this treatment.

An AE can therefore be any unfavourable and unintended sign [including an abnormal laboratory finding, for example], symptom, or disease temporally associated with the use of a medical product, whether or not considered related to the medical product.

An Adverse Drug Reaction [ADR] is defined as any untoward and unintended responses to an investigational medicinal product related to any dose administered

In accordance with the above definition, adverse events may include:

- Worsening [change in nature, severity or frequency] of conditions present at the onset of the study
- Condition detected or diagnosed after study drug administration even though it may have been present prior to the start of the study

An AE does not include:

- Medical or surgical procedures (e.g. surgery, endoscopy, tooth extraction, transfusion), the condition that leads to the procedure is an adverse event.
- Pre-existing diseases or conditions present or detected prior to start of the study drug administration that does not worsen.
- Situations where an untoward medical occurrence has not occurred (e.g. hospitalization for elective surgery, social and / or convenience admissions).

A Serious Adverse Event [SAE] is any untoward medical occurrence that at any dose:

- Results in death
- Is life threatening*
- Results in persistent or significant disabling / incapacity
- Requires in-patient hospitalization or prolongation of existing hospitalization[#]
- Occurrence of congenital anomaly or birth defect if relevant
- Other important medically significant events that may not result in death, be immediately life threatening, or require hospitalization, may be considered an SAE when, based upon appropriate medical judgment, they may jeopardize the well-being of the subject and may require medical or surgical intervention to prevent one of the outcomes listed in this definition. Examples of such events are intensive treatment in an emergency room or at home for allergic bronchospasm; blood dyscrasias, or

convulsions that do not result in hospitalization; or development of drug dependency or drug abuse.

*The term "life-threatening" in the definition of "serious" refers to an event in which the subject was at risk of death at the time of the event; it does not refer to an event which hypothetically might have caused death if it were more severe.

#“Inpatient hospitalization” does not imply that the subject must have had an overnight stay in the hospital. If the subject was admitted to the hospital for less than a day for the purpose of treatment or observation, the definition of “Inpatient hospitalization” is met, **provided** the subject is admitted solely for treatment of the event and not admitted for any social reasons, ease of compliance, day care procedures, or for medical or hospital records (insurance reimbursement) purpose. Although, brief treatment in an outpatient clinic or Emergency department does not constitute “inpatient hospitalization”, depending on the intervention/treatment required for the event, it may satisfy the criteria of inpatient hospitalization to be reported as an SAE.

An Unexpected Adverse Drug Reaction is an adverse reaction, the nature or severity of which is not consistent with the applicable product information [e.g., Prescribing Information]

Events previously unobserved or undocumented must be classified as unexpected on this basis, and not on the basis of what might be anticipated from the pharmacological properties of a medicinal product.

The Investigator should attempt to establish a diagnosis of the event based on signs, symptoms, and/or other clinical information. In such cases, the diagnosis should be documented as the AE/SAE and not the individual signs/symptoms.

b. Classification of Adverse Events

All adverse events will be classified, MedDRA coded (Version 17.0 or higher) and documented as per the grading system presented in NCI CTCAE v5.0.

In the course of the study, if adverse events are not covered in the NCI CTCAE v5.0 occur the Investigator will determine the severity of these adverse events as follows:

- Mild: Awareness of symptoms but easily tolerated
- Moderate: Discomfort enough to cause interference with usual activity
- Severe: Incapacitating with inability to work or carry out usual activity
- Life threatening
- Death related

The SAE will not be closed out if it is of changing severity during the course. It will be reported with changes in the severity as it upgrades in follow up reports such that each upgraded sequelae will not be recorded as a new SAE but continuation of same SAE and the serious and unexpected adverse

reactions will be reported to DCGI within the stipulated timeline. Only the highest grade of severity will be considered for analysis purpose.

c. Clarification in Reporting of Deaths

All subject deaths (regardless of relationship to study drug) should be reported for subjects while on the study protocol. This should be recorded on the end of study CRF page and the SAE form. If a subject dies after signing consent but before the first dose of the study drug, this will also be recorded in the CRF. Death is an outcome of an adverse event and not an adverse event in itself. All reports of subject death should include an adverse event term (other than “Death”) for the cause of the death. If an adverse event term is not provided, the treating physician will be queried to obtain the cause of death. Only in the rare occurrence that no verbatim description of an adverse event can be obtained from the investigative site, will “Death-Unknown cause” be used as the event term.

d. Causality of the adverse event:

The Investigator’s causality assessment should consider the potential etiologies for the observed adverse event. An adverse event may be related to the study drug, other concomitant medications, the underlying disease pathology, inter-current illness, a procedure performed in the course of the study, or another reason. Among the potential etiologies, the investigator should make a determination based on the most likely causal relationship. When a causality assessment is provided for a SAE, it is important to include a rationale for the assessment so that a better understanding of the reported event can be compiled. The rationale should be accompanied by all available supporting evidence, including relevant laboratory tests, histopathology evaluations and the results of other diagnostic procedures.

The Investigator will make a judgment considering whether or not, in his opinion, the adverse event was related to the drug according to the following classification.

The likelihood of the relationship of the adverse event to the study drug is to be recorded as follows.

Certain: A clinical event, including laboratory test abnormality, occurring in a plausible time relationship to drug administration and which cannot be explained by concurrent disease or other drugs or chemicals. The response to withdrawal of the drug [de-challenge] should be clinically plausible. The event must be definitive pharmacologically or as a logical phenomenon, using a satisfactory re-challenge procedure if necessary.

Probable /Likely: A clinical event, including laboratory test abnormality, with a reasonable time sequence to administration of the drug, unlikely to be attributed to concurrent disease or other drugs or chemicals and which follows a clinically reasonable response on withdrawal [de-challenge]. Re-challenge information is not required to fulfill this information.

Possible: A clinical event, including laboratory test abnormality, with a reasonable time sequence to administration of the drug , but which could also be explained by concurrent disease or other drugs or chemicals. Information on drug withdrawal may be lacking or unclear.

Unlikely: A clinical event, including laboratory test abnormality, with a temporal relationship to drug administration which makes a causal relationship improbable, and in which other drugs, chemicals or underlying disease provide plausible explanations.

Unrelated: Event or laboratory test abnormality – is clearly NOT related to the investigational agent(s)

e. Laboratory Abnormalities

Abnormal laboratory findings (e.g., biochemistry, hematology) or other abnormal assessments (e.g., electrocardiogram, X-rays, vital signs) per se are not reported as AEs. However, abnormal findings that are deemed clinically significant must be recorded as AEs if they meet the definition of an adverse event (and recorded as an SAE if they meet the criteria of being serious) as described previously, as per the classifications accorded in NCI CTCAE v5.0 for laboratory AEs.

Clinically significant abnormal laboratory or other abnormal findings that are detected after study drug administration or that are present at baseline and worsen following the administration of study drug are included as AEs (and SAEs if serious). The Investigator should exercise his or her medical judgment in deciding whether an abnormal laboratory finding or other abnormal assessment is clinically significant. Usually, the abnormality should be associated with a clinically evident sign or symptom, or be likely to result in an evident sign or symptom in the near term, to be considered clinically significant.

f. Documentation of Adverse Events

Any AE occurrence during the study must be documented in the subject's medical records in accordance with the Investigator's normal clinical practice and on the AE page of the CRF. SAEs that occur during the study must be documented in the subject's medical record, on the AE page of the CRF and on the SAE form of the CRF.

The Investigator should attempt to establish a diagnosis of the event based on the signs, symptoms and/or other clinical information. In such cases, the diagnosis should be documented as the AE (and SAE if serious) and not the individual signs/symptoms. If a clinically significant abnormal laboratory finding or other abnormal assessment meets the definition of an AE, then the AE page of the CRF must be completed as appropriate. In addition, if the abnormal laboratory finding meets the criteria for being serious, the SAE form must also be completed. A diagnosis, or clinical signs or symptoms if the diagnosis is unknown, rather than the clinically significant laboratory finding or abnormal assessment, should be used to complete the AE/SAE page. As additional information becomes available and a diagnosis is achieved, the signs/symptoms or abnormal finding verbatim should be updated on the CRF.

If no diagnosis is known and clinical signs or symptoms are not present, then the abnormal finding should be recorded on the AE/SAE page. If an SAE report is completed, pertinent laboratory data should be recorded on the SAE form, preferably with baseline values and copies of laboratory reports. The SAE form should be completed as thoroughly as possible. It is very important that the

Investigator provide an assessment of the causal relationship between the event and the study drug at the time of the initial report.

g. Follow-up of Adverse Events and Serious Adverse Events

Subjects will be monitored for adverse events/reactions to the study drug and/or study procedures during the study product administration. All AEs related to ALZUMAbTM and all SAEs must be followed until resolution, until the condition stabilizes, until the event is otherwise explained, or until the subject dies or is lost to follow-up. The investigator will administer appropriate treatment for the SAE resolution. The Investigator is responsible to ensure that follow-up includes any supplemental investigations as may be indicated to elucidate as completely as practical the nature and/or causality of the AE/SAE. This may include additional laboratory tests or investigations, histopathological examinations, or consultation with other health care professionals.

h. SAE/SADRs reporting (Investigator's Responsibilities)

All study drug related SAEs (SADRs), occurring **after the patient signs the informed consent and until the one year follow-up period is over or until the patient has prematurely stopped participation in the study** must be reported to drug manufacturer (Biocon Ltd) within 24 hours of learning of its occurrence.

Recurrent episodes, complications, or progression of the initial SADRs must be reported as follow-up to the original episode within 24 hours of the Investigator receiving the follow-up information. An SADR occurring at a different time interval should be reported separately as a new event.

Information about all SADRs is collected and recorded on the Serious Adverse Event Report Form. The Investigator must assess the relationship to drug and report all SADRs by completing the SAE Report Form in English, and send the completed, signed form within 24 hours to Biocon Ltd. The original SAE Report Form and the fax confirmation sheet must be kept with the documentation at the site. The investigator should notify all SADRs to Biocon through email. The telephone and fax number of the contact persons listed below for SADRs reporting can be used as alternate modes of communication.

The Investigator must **inform one of the responsible persons** of Biocon Ltd (Pharmacovigilance personnel listed below) **by telephone as soon as possible and not later than 24 hours** of the occurrence of an SADR.

Questions pertaining to a specific serious adverse drug reaction occurring in a patient should be directed to the contact persons listed in the protocol.

Follow-up information should be sent to Biocon Ltd PVD (where the original SAE Report Form was sent), using a new SAE Report Form stating that this is a follow-up to the previously reported SAE and giving the date of the original report. Each re-occurrence, complication, or progression of the original event should be reported as a follow-up to that event even if it occurs at a different time interval. The follow-up information should describe whether the event has resolved or continues, if and how it was treated, and whether the patient continued or withdrew from surveillance participation. If there are SADR/SAEs, they should be intimated to all the other IRB/IEC through the sites. They should be intimated to the other sites within 14 calendar days of SAE/SADR occurrence and the sites will in turn inform the IRB/IEC within 24 hours of getting the information.

If the SAE/SADRs is not previously documented in Package Insert (unexpected, new occurrence) a Biocon PVD personnel or designee may urgently require further information from the Investigator for Health Authority reporting. All SAE/SADRs will be reported to DCGI, and relevant IRB/IEC by the Investigator within 24 hours (first intimation) and due analysis within 14 days of first awareness of the event in required format as per the New Drugs and Clinical Trials 2019. The same guiding principle as described above for initial and follow up reports of SAE/SADRs will be followed for SAE/SADRs reporting to DCGI and IRB/IEC. Any report of the SAE/SADRs, after due analysis shall be forwarded by the sponsor to the DCGI, IRB/IEC where the trial has been conducted, within fourteen days of knowledge of occurrence of the serious adverse event as specified in Table 5 (as per the timeline for marketed products in New Drugs and Clinical Trials 2019).

All study drug related Serious Adverse Events should be reported by the Investigator to Biocon Pharmacovigilance department and email address given below:

Pharmacovigilance Department

Clinical Development & Medical affairs,
Biocon Biologics India Limited,
[name]
[name]

Email: [contact]

[contact]

Toll Free No: [name]

It should be sent within 24 hours of the occurrence of the event.

To ensure the patient safety each pregnancy in a patient occurring after the patient begins taking drug until the treatment is stopped should be reported to the above contact details of Biocon Pharmacovigilance within 24 hours of learning of its occurrence. The pregnancy should be followed to determine the outcome including the spontaneous or voluntary termination, details of birth, the presence of any birth defects, congenital abnormalities. Any patient in whom pregnancy occurs after signing of the informed consent form and before the patient is enrolled should be excluded from the surveillance.

The cases of pregnancy reported by female patients or female partners of male patients will be followed up till the outcome. Investigator should fill the Pregnancy Reporting Form and send to the above mentioned personnel. Pregnancy follow up should be recorded in the same form and should include an assessment of the possible relationship to ALZUMAbTM of any pregnancy outcome. The Investigator should arrange for the appropriate counseling of patients to discuss the implications of continuing or terminating pregnancy.

Pregnancies occurring during the post-treatment follow-up shall be reported and followed up if suspected to be unintended pregnancies related to ALZUMAbTM or are associated with abnormal outcome, birth defect or congenital anomaly related to ALZUMAbTM.

i. Infusion Reactions

During administration of ALZUMAb™ some patients may develop infusion reactions. Infusion reactions are most likely to occur during the first cycle of dosing and tend to decrease in severity and frequency upon subsequent infusions. Acute infusion-related reactions are expected with Itolizumab administration. Symptoms may include nausea, flushing, urticaria, cough, hypersensitivity, pruritus, rash, wheezing, dyspnea, dizziness, headache, and hypertension. Acute infusion reactions should be treated using the standard of care; and physicians may need to delay dosing till the patient is stabilized.

ii Overdose Treatment:

Since the investigational products are directly administered by personnel involved in the study in controlled manner, overdose is unlikely to occur. However, in case of overdose, the management will be as per standard of care. In case there is overdose, the same should be informed to sponsor safety team on real time basis. Overdose with associated adverse events should be informed to sponsor safety team in line with AE/SAE reporting timelines (as applicable).

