8.1 Schedule of Study Visits and Procedures

Visit	S1	W1	W2	W3	W4	End of Study
Weeks	-2 to 0	0	1	2	3	4 th week
Days	-14	1 [^]	8 [^]	15 [^]	22 [^]	30 [#]
Event						
Informed Consent	X					
Medical History	X					
Inclusion/Exclusion Criteria ^a	X					
Weight	X	X	X	X	X	X
Physical Examination, Vital signs ^{\$}	X	X	X	X	X	X
Hematology* [;] ^{\$}	X	X	X	X	X	X
Biochemistry** [;] ^{\$}	X	X	X	X	X	X
Chest X Ray/CT scan ##	X	X	X	X	X	
Randomisation	X					
Best Supportive Care		X	X	X	X	
Pre-medication @ in Arm A		X	X	X	X	
ALZUMAb infusion ^b		X	X	X	X	
Cytokines and Immunophenotyping assessment	X	X ^d				
PaO ₂ /FiO ₂ ratio	X	X	X	X	X	
CRP	X	X	X	X	X	X
Daily Morning SOFA Score ^c	X	X	X	X	X	
Concomitant medication check	X	X	X	X	X	X
Adverse events	X	X	X	X	X	X

[^] Window period: ± 48 Hours.

^a All inclusion / Exclusion criteria to be reviewed prior to first dosing. Screening period is up to 14 days however screening and baseline visit can happen in one day and screening assessment can be considered as baseline assessments.

^b 1.6 mg/kg dose iv infusion, if well tolerated and improvement in patient observed, investigator has the discretion to continue with 1.6 mg/kg dose every 2 weeks or 0.8 mg/kg weekly regimen in combination therapy with standard of care (anti-viral and antibiotic drugs). Subsequent dose and frequency can be modified, deferred or stopped if patient recovers as per investigator's

discretion. If patients' overall parameters improve (if performed and RT-PCR is negative) further dose need not be given. Total infusion received during study duration can vary from 1 to 4 for each patient. If patient recovers/is discharged earlier than 30 days, then patient should be contacted telephonically to get status of the patient on 30th day after enrolment.

c: Daily SOFA Scoring until patient moved out of ICU/equivalent, and later SOFA score frequency as per investigator discretion. If patient is not admitted in the ICU/equivalent at the time of enrolment, then it is recommended to capture these assessments daily for first 7 days.

Window period for assessment at 4th week or 30th day is \pm 3 days.

*Hematology assessments (blood test) include: hemoglobin, total leukocyte count, differential count, absolute neutrophil count, absolute lymphocyte count, and platelet count.

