## **10 Other Evaluations**

### **Additional Safety Evaluation**

Additional safety analysis will be provided by treatment group, by severity, by outcome and related to study drug. Events will be summarized with descriptive statistics (count & percentage).

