### 14.3.5 Treatment Emergent Adverse Event (TEAE) by Outcome

ARM	System Organ Class	Preferred term	Recovered/resolved	Recovering/resolving	Not recovered/not resolved	Recovered/resolved with sequelae	Fatal	Unknown

Arm A (N=XX)	Any SOC		XX (XX.X %)	XX (XX.X %)	XX (XX.X %)	XX (XX.X %)	XX (XX.X %)	XX (XX.X %)
		PT1	XX (XX.X %)	XX (XX.X %)	XX (XX.X %)	XX (XX.X %)	XX (XX.X %)	XX (XX.X %)
		PT2	XX (XX.X %)	XX (XX.X %)	XX (XX.X %)	XX (XX.X %)	XX (XX.X %)	XX (XX.X %)
	SOC1		XX (XX.X %)	XX (XX.X %)	XX (XX.X %)	XX (XX.X %)	XX (XX.X %)	XX (XX.X %)
		PT1	XX (XX.X %)	XX (XX.X %)	XX (XX.X %)	XX (XX.X %)	XX (XX.X %)	XX (XX.X %)
		PT2	XX (XX.X %)	XX (XX.X %)	XX (XX.X %)	XX (XX.X %)	XX (XX.X %)	XX (XX.X %)
		PT3	XX (XX.X %)	XX (XX.X %)	XX (XX.X %)	XX (XX.X %)	XX (XX.X %)	XX (XX.X %)
Arm B (N=XX)	Any SOC		XX (XX.X %)	XX (XX.X %)	XX (XX.X %)	XX (XX.X %)	XX (XX.X %)	XX (XX.X %)
		PT1	XX (XX.X %)	XX (XX.X %)	XX (XX.X %)	XX (XX.X %)	XX (XX.X %)	XX (XX.X %)
		PT2	XX (XX.X %)	XX (XX.X %)	XX (XX.X %)	XX (XX.X %)	XX (XX.X %)	XX (XX.X %)
	SOC1		XX (XX.X %)	XX (XX.X %)	XX (XX.X %)	XX (XX.X %)	XX (XX.X %)	XX (XX.X %)
		PT1	XX (XX.X %)	XX (XX.X %)	XX (XX.X %)	XX (XX.X %)	XX (XX.X %)	XX (XX.X %)
		PT2	XX (XX.X %)	XX (XX.X %)	XX (XX.X %)	XX (XX.X %)	XX (XX.X %)	XX (XX.X %)
		PT3	XX (XX.X %)	XX (XX.X %)	XX (XX.X %)	XX (XX.X %)	XX (XX.X %)	XX (XX.X %)

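### Follow-up to resolution depends on relatedness to itolizumab, so open non-serious AEs may be resolved more completely in Arm A than in Arm B when SAP Table 14.3.5 compares outcomes

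*Protocol*

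**What the plan says.** Protocol Appendix 3 g opens with "Subjects will be monitored for adverse events/reactions to the study drug and/or study procedures during the study product administration" and continues: "All AEs related to ALZUMAbTM and all SAEs must be followed until resolution, until the condition stabilizes". That duty also ends if the event is otherwise explained, or if the subject dies or is lost to follow-up.

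Other parts of the protocol apply to both arms. Appendix 3 f states "Any AE occurrence during the study must be documented in the subject's medical records". The AE row of the schedule in section 8.1 is marked from screening to the Day 30 visit with no arm restriction. Footnote b of that schedule says that if a patient recovers or leaves hospital before 30 days, "then patient should be contacted telephonically to get status of the patient on 30th day after enrolment". It does not name AE outcome as something to ask about.

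SAP section 10 states: "Additional safety analysis will be provided by treatment group, by severity, by outcome and related to study drug". The shell for Table 14.3.5, "Treatment Emergent Adverse Event (TEAE) by Outcome", has one block per arm, with columns for recovered, recovering, not recovered, recovered with sequelae, fatal and unknown. It gives no date at which the outcome is read.

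**The concern.** When AE outcome is compared by arm, each arm's events should be followed with the same effort and to the same point. Here the effort for a non-serious event depends on whether it is attributed to itolizumab, and that attribution is available in one arm only. The trial is open label (SAP 4.1), so the judgement is made with the arm known.

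At stake are the recovering, not recovered and unknown columns of Table 14.3.5 for non-serious events. A difference there could reflect how long the site had to pursue the event rather than how it went clinically. Safety is part of the primary objective (Protocol section 4), so readers will look at this table even though it carries no test.

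**Working it through.** There is no figure in the plan to reproduce. The check is mainly a reading of the passages against each other.

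**1. Which events the Appendix 3 g rule covers**

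| Event | Arm A | Arm B |
|---|---|---|
| Serious, related or not | Covered | Covered |
| Non-serious, related to itolizumab | Covered | Cannot arise: drug not given |
| Non-serious, unrelated | Not covered | Not covered |

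The arms differ only in the middle row. The shell of SAP Table 14.3.4 prints a related column for Arm B, but Arm B receives best supportive care alone (Protocol section 7).

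**2. Whether the schedule closes the gap**

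While a patient attends visits it largely does, because AEs are reviewed in both arms to Day 30. It does not do so after early discharge, which the plan expects: the footnote to SAP Table 14.1.2 provides for patients sent home early because of clinical improvement and government policy. From then on, a related Arm A event must still be pursued. A non-serious Arm B event waits for a call that need not mention it. After Day 30 the former may still be followed and the latter is not.

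**3. Whether another passage closes it**

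- Appendix 3 f says that CRF entries should be updated as information arrives. That sentence is about replacing signs and symptoms with a diagnosis, not about AE outcome.
- SAP section 13 censors patient data at the last assessment or after 30 days of enrolment. The surrounding text is about deaths and loss to follow-up. Even if the limit governed AE outcome, the interval between discharge and Day 30 would remain.
- The time frame for treatment-related side effects in Protocol section 5 runs to 30 days after the last dose and is starred for both arms. Arm B has no dose, so this gives no common cut-off.

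**4. What would determine the size**

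Let *r* be the share of non-serious Arm A events judged related. Let *u* be the share of non-serious events left open or unknown where no duty to follow to resolution applies. Suppose *u* is the same in both arms and no related event is left open. Then:

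- Arm A open share = (1 − *r*) × *u*
- Arm B open share = *u*
- Difference (B − A) = *r* × *u*

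The documents give neither input for this population. With assumed values:

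| *r* | *u* | Arm A open | Arm B open | Difference |
|---|---|---|---|---|
| 0.1 | 0.1 | 9% | 10% | 1 point |
| 0.3 | 0.2 | 14% | 20% | 6 points |
| 0.5 | 0.2 | 10% | 20% | 10 points |
| 0.6 | 0.4 | 16% | 40% | 24 points |

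This is the formula evaluated over a wide assumed range, not an estimate. For a given *r* and *u* it is also a maximum, because the rule itself lets follow-up end at stabilisation or loss to follow-up, so some related events would still not show as recovered.

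**5. Scale of the table**

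About 30 patients at 2:1 gives 30 × 2/3 = 20 in Arm A and 30 × 1/3 = 10 in Arm B. If percentages are of patients, one patient is 1/10 = 10 points in Arm B and 1/20 = 5 points in Arm A. One or two open entries would be visible, whatever their cause.

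**The case against.** The strongest reply is that few events are affected. AEs are documented and reviewed in both arms to Day 30, and Listings 16.1.14 and 16.1.15 carry end date and outcome for everyone. The inequality touches only related, non-serious Arm A events that are still open when scheduled contact ends. Many of these may be infusion reactions, which have no counterpart in Arm B and pass quickly. In the psoriasis phase 3 study in Appendix 4, acute infusion reactions occurred in 18 and 15 of 90 patients in the two itolizumab arms. Related AEs occurred in 26.7% and 28.9%, that is 0.267 × 90 = 24 and 0.289 × 90 = 26 patients. If all those reactions were judged related (an assumption), they could account for 18/24 = 75% and 15/26 = 58% of patients with a related AE. The phase 2 infusion reactions all resolved. Such events would show as recovered under either rule. Table 14.3.5 is also descriptive, and AE outcome is not an endpoint.

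All of this stands as a limit on the size. It does not make the rule equal, and it does not supply the missing question in the Day 30 call or a date for the table.

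A reader might go further and infer that Arm A also has longer to reach a higher worst grade, so that Table 14.3.3 is distorted against the drug. The documents do not support that. The SAP tabulates by severity without a worst-grade rule. The protocol sentence "Only the highest grade of severity will be considered for analysis purpose" (Appendix 3 b) closes a paragraph about SAEs, and SAEs are followed in both arms.

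**Conclusion.** The point holds in a limited form and is minor. The follow-to-resolution rule is unequal by arm for non-serious events, and the SAP compares AE outcome by arm without a common date. The likely direction is more complete resolution in Arm A, with relatively more recovering, not recovered or unknown entries in Arm B. That is a possibility, not a certainty. Deaths and serious events are not affected.

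The size cannot be determined from the documents and is probably small. That judgement rests on in-hospital review to Day 30 in both arms, on many related events being short-lived (an assumption), and on the table being descriptive.

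Two further inferences should be resisted. One is that Arm B has no follow-up at all: what it lacks is a duty to follow non-serious events to resolution, and unrelated non-serious events in Arm A lack it equally. The other is that the psoriasis AE rates in Appendix 4 measure the bias. They are patient-level figures over 52 weeks in another disease and say nothing about events open at discharge or Day 30 in COVID-19.

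**What to change.** Keep the Appendix 3 g sentence as it is for pharmacovigilance. Replacing it would remove the longer follow-up of related AEs and SAEs. Add a sentence beside it: the status of every AE in both arms, whatever its relatedness, is ascertained up to resolution or Day 30/EOS, whichever comes first. In section 8.1 footnote b, add that the Day 30 call asks about any AE still open.

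In SAP Table 14.3.5, and in Table 14.3.3 for consistency, tabulate outcome and grade as of Day 30/EOS in both arms. Put later follow-up of related AEs and SAEs in a separate listing.

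The cost is one protocol sentence, one question in a call already planned, a cut-off in two tables and one listing. The downside is a few more AE status updates for sites, and resolutions after Day 30 will appear only in the listing. The change equalises ascertainment. It does not remove real differences in the kinds of event, such as infusion reactions in Arm A only, and the table should still be read with that in mind.
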